9.2 Secondary Analyses

There are both efficacy and safety endpoints. All secondary safety analyses will be conducted on the Safety Population.

Secondary efficacy analyses will be summarized with categorical descriptive statistics for the following:

- The amount of product used per year as part of at-home prophylaxis and therapy for bleeding episodes, and
- A physician's qualitative assessment of hemostasis (evaluated as "None", "Moderate", "Good", or "Excellent" in response to therapy with Alphanate® received by the subject in a hospital or another location under the physician's direct supervision).

Secondary safety analyses will be summarized with categorical descriptive statistics for the following:

- The frequency, nature, causality and severity of adverse events,
- The occurrence of changes in biochemical parameters which would indicate renal or hepatic impairment,
- The incidence of seroconversion to human immunodeficiency virus type 1 and 2 (HIV-1/HIV-2), hepatitis A virus (HAV), hepatitis B virus (HBV), hepatitis C virus (HCV) or parvovirus B19 in subjects seronegative for these viruses at the time of enrollment,

9.2.1 Adverse Events

All reported terms (Investigator descriptions) for adverse events (AEs) will be coded using Version 13.0 of the Medical Dictionary for Regulatory Activities (MedDRA). The incidence of treatment-emergent AEs (TEAEs) will be summarized as those events that occur on or after the date of the first dose of study drug.

CONFIDENTIAL

AE data will be listed individually and summarized by body system organ class (SOC) and preferred terms within system organ class. Each AE will be counted only once for a given subject. If the same AE occurs on multiple occasions, the highest severity and least favorable relationship will be assumed. If two or more AEs are reported as a unit, the individual terms will be reported as separate experiences.

All AEs will be included in the data listings.

9.2.2 Serious Adverse Events and Death

A data listing of all Serious Adverse Events (SAEs), including treatment-emergent SAEs, will be presented. SAEs with onset prior to receiving study medication or after discontinuation of study medication will be excluded from the descriptive summaries.

A separate listing will be presented for all deaths as well as events leading to discontinuation. Complete narratives will be included for deaths.

9.3 Additional Analyses

9.3.1 Exposure to Study Drug

Total exposure through the number of Factor VIII units infused will be summarized with descriptive statistics by dosing. Frequencies and percentages will also be used to summarize the number of infusions at each dosing.

Exposure to study drug will be listed for each subject to indicate the complete usage pattern including number of exposures at home and in clinic, reason for infusion, whether hemostasis was achieved (if evaluation available) and physician comments.

9.3.2 Laboratory Evaluations

Descriptive summaries of quantitative clinical laboratory results will be presented by nominal study visit for change from baseline. Laboratory results will include Factor VIII findings, biochemistry, hematology, immunological status and viral serology.

A data listing will be included that displays all laboratory panels and test values.

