9. Viral and serological tests will be conducted: including testing for HBsAg, and for antibodies to HAV, HBcAb, HBsAb, HCV, HIV-1/HIV-2 and parvovirus B19 (by routine immunoassay).
10. A sample of venous blood will be drawn from which approximately 5 mL of serum will be prepared and aliquoted into three vials of at least 1.5 mL of sample each. The samples will be frozen and retained at -20°C in the event that they are required for later serological or virology tests.

Contains Confidential and Proprietary Information of Grifols Inc.

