8.2 Secondary Endpoints

All subjects will be considered to be evaluable for the secondary endpoints.

1. The frequency, nature, causality and severity of adverse events.
2. The occurrence of variations in biochemical parameters which would indicate renal or hepatic impairment.
3. Evidence for seroconversion to HIV-1/HIV-2, HAV, HBV, HCV and parvovirus B19 for subjects who are seronegative for these viruses upon enrollment.
4. The amount of product used per year as part of at-home prophylaxis and therapy for bleeding episodes.
5. A physician's qualitative assessment of hemostasis (evaluated as "None," "Moderate," "Good," or "Excellent") in response to therapy with Alphanate[®] received by the subject in a hospital or at another location under the physician's direct supervision.

With this section, the design of this clinical trial satisfies the recommendations of the CPMP for trials in previously-treated patients of concentrates with marketing authorization in which a manufacturing process has been added.

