9.2.2 Secondary Endpoints

1. Adverse Events

The percentage of subjects experiencing one or more adverse events will be calculated. The frequency of adverse events will be reported as a proportion of the total number of infusions with Alphanate®. Causality [the proportions of adverse events judged to be definitely, probably, possibly, probably not and definitely not related to treatments with Alphanate®] and severity will be reported as percentages of the total number of adverse events occurring during the course of the clinical trial.

2. Assessment of Biochemical Tests on Serum

Descriptive statistics will be presented, with a focus on parameters which when elevated may indicate alterations in hepatic or renal function.

3. Viral Safety

Viral safety will be determined by a lack of seroconversion to reactivity against the specific blood-borne viruses for which subjects will have been tested and found to be nonreactive at the time of enrollment.

4. Consumption Analysis

Descriptive statistics will be employed to evaluate the use of Alphanate® by subjects, both for self-administration and for treatment by the investigator at the clinical site or other places of treatment.

5. Hemostasis

Descriptive statistics will be employed to evaluate the physicians' qualitative assessments of the ability of Alphanate® to control bleeding episodes when administered at the clinical site.

Contains Confidential and Proprietary Information of Grifols Inc.

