6.3 Subgroups

There are no planned subgroup analyses.

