6.6 Statistical Notation and Methodology

Unless stated otherwise, the term “descriptive statistics” refers to the number of subjects (n), mean, median, standard deviation (SD), minimum, and maximum for continuous data and frequencies and percentages for categorical data. Unless otherwise noted, all data collected during the study will be

CONFIDENTIAL

included in data listings and will be sorted first by subject number and then by date within each subject number.

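### The renal and hepatic endpoint is an occurrence in individual subjects, but the SAP defines no qualifying change and plans only a by-visit table of change from baseline, which cannot give the number affected

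*SAP*

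**What the plan says.** **Endpoint.** Protocol 8.2 lists "The occurrence of variations in biochemical parameters which would indicate renal or hepatic impairment" as a secondary endpoint and treats all subjects as evaluable for it. SAP 9.2 has almost the same item: "The occurrence of changes in biochemical parameters which would indicate renal or hepatic impairment". Protocol section 4 speaks of altered function rather than impairment. Protocol 9.1 ties the sample of 50 to 80 evaluable patients, followed for at least two years, partly to renal or hepatic function.

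**Method.** Protocol 9.2.2 says "Descriptive statistics will be presented, with a focus on parameters which when elevated may indicate alterations in hepatic or renal function". SAP 9.2 introduces its list of secondary safety endpoints with "Secondary safety analyses will be summarized with categorical descriptive statistics for the following". SAP 9.3.2, under Additional Analyses, then says "Descriptive summaries of quantitative clinical laboratory results will be presented by nominal study visit for change from baseline". For continuous data, SAP 6.6 states that the term descriptive statistics "refers to the number of subjects (n), mean, median, standard deviation (SD), minimum, and maximum for continuous data".

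**Displays.** SAP 11.1 lists one biochemistry table (12.8), a listing of all biochemistry results (12.21) and a listing of abnormal ones (12.22). It lists no incidence table and no shift table for biochemistry.

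**Visits.** Protocol 7.5 requires serum chemistry at every unscheduled visit. SAP 7.2 defines windows only for the post-infusion visit and the quarterly visits.

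**HCV.** Screening tests for "antibodies to HAV, HBcAb, HBsAb, HCV, HIV-1/HIV-2 and parvovirus B19 (by routine immunoassay"). The entry criteria do not exclude HCV-positive subjects. On subgroups, SAP 6.3 says "There are no planned subgroup analyses".

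**The concern.** An occurrence endpoint is answered by a number of subjects out of a denominator. To produce it, the analyst needs a rule that makes a result a qualifying change, and a table that counts each subject once. The plan has neither. The one analysis it does specify describes the distribution of changes at each visit, which answers a different question.

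As written, the study report could complete every display in SAP 11.1 and still not state how many subjects showed signs of renal or hepatic impairment. If the rule is chosen after the laboratory data have been seen, the count will depend on that choice.

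**Working it through.** The documents give no figure for this endpoint, so there is none to reproduce. The check sets the plan's parts side by side and tests what table 12.8 can and cannot convey.

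**1. Endpoint against display.** The other two laboratory event endpoints each have a general data summary and a separate event table in SAP 11.1: 12.7 and 12.13 for inhibitors, 12.11 and 12.14 for viral infection. Biochemistry has only 12.8. No section gives a multiple of normal, a multiple of baseline, a grade or a persistence rule.

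**2. What table 12.8 shows for one large rise.** Assume one subject's ALT goes from 30 to 300 U/L at a scheduled visit and nobody else changes. These values are illustrative. The rise is d = 300 − 30 = 270.

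| Statistic of change | Formula | n = 50 | n = 80 |
|---|---|---|---|
| Mean | d/n | 5.4 | 3.4 |
| SD | d/√n | 38.2 | 30.2 |
| Maximum | d | 270 | 270 |

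The mean barely moves, but the maximum shows the rise.

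**3. What it cannot count.** Quarterly visits to month 30 give 30/3 = 10 visits. Keep n = 50 and d = 270, with all other changes zero.

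- Case A: one subject is raised at all ten visits.
- Case B: ten subjects are each raised once, at ten different visits.

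At every visit both cases give mean 5.4, median 0, SD 38.2, minimum 0 and maximum 270, so the tables are identical. The endpoint is 1/50 = 2% in case A and 10/50 = 20% in case B. With 80 subjects it is 1/80 = 1.25% against 10/80 = 12.5%. With only the eight visits to month 24 (24/3) and 50 subjects, it is 2% against 8/50 = 16%.

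**4. What it cannot relate to baseline.** A change of +60 U/L is 30 to 90 (90/30 = 3 times baseline) in one subject and 150 to 210 (210/150 = 1.4 times) in another. The change table records both as +60. These values are again illustrative.

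**5. Unscheduled visits.** A ±10-day window covers 21 days of a quarter of about 91 days. The other (91 − 21)/91 = 77% of calendar time lies in no quarterly window. Biochemistry drawn then has no assigned nominal visit, so it need not reach even the maximum.

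**6. Pooling over HCV status.** The documents give neither an HCV-positive share nor an SD, so this rests on assumptions. One visit was simulated with n = 50 (20,000 runs). Changes were normal, with SD 0.2 × ULN (upper limit of normal) in HCV-negative and 0.5 or 1.0 × ULN in HCV-positive subjects. One HCV-negative subject had a rise. Entries are the share of runs in which the statistic exceeded its own 95th percentile without the rise. Ranges run over the two SDs.

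| HCV-positive share | Mean, rise 2 × ULN | Mean, rise 5 × ULN | Maximum, rise 2 × ULN | Maximum, rise 5 × ULN |
|---|---|---|---|---|
| 0% | about 40% | 97% | 100% | 100% |
| 30% | 13–22% | 34–71% | 5–100% | 100% |
| 60% | 10–17% | 23–54% | 5–100% | 100% |

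Large rises always show in the maximum. Moderate ones can be masked if HCV-positive subjects vary widely. Neither statistic is a count.

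**7. What a count would give.** Exact (Clopper-Pearson) one-sided 95% upper limits for illustrative counts:

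| Subjects affected | n = 50 | n = 80 |
|---|---|---|
| 0 | 5.8% | 3.7% |
| 1 | 9.1% | 5.8% |
| 2 | 12.1% | 7.7% |

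For zero events, a two-sided 95% interval has upper limit 1 − 0.025^(1/n): 7.1% at n = 50 and 4.5% at n = 80.

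**The case against.** The sponsor can fairly say that SAP 9.2 already commits to a categorical summary, that 9.3.2 is an additional analysis, and that individual data are not lost. Listings are sorted by subject and date, and 12.21 and 12.22 show each subject's course. Protocol 10.1 requires any substantive new abnormality to be recorded and followed, so a marked rise may also reach the adverse event tables, which count each event once per subject. The study is uncontrolled, and SAP 6.4 calls the analysis primarily descriptive.

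Much of this stands. It rules out several stronger readings that a reader might infer:

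- *That the table hides the event.* It is not limited to means. The maximum would expose a large rise at a scheduled visit.
- *That a mean shift of 5.4 U/L is lost in ordinary scatter.* The documents give no SD, so this cannot be asserted. With no HCV-positive subjects, the simulated mean itself usually registered a 5 × ULN rise.
- *That baseline HCV serology goes unused.* It defines who is at risk for the HCV seroconversion endpoint.
- *That a new infection could not be told apart from underlying liver disease.* Viral serology is quarterly, serum is stored, and seroconversion has its own displays.
- *That stable chronic HCV disease distorts the change table.* Each subject is his own control, so a steady elevation contributes about zero change.

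The gap remains. A categorical promise without categories cannot be programmed. The word may also be loose, since SAP 9.2 applies it to annual product use, which is a quantity. Listing 12.22 does not define abnormal and is not a summary. The adverse event route depends on the investigator's judgement, and both documents list this endpoint separately from adverse events.

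**Conclusion.** The concern holds as a gap between endpoint and analysis. The endpoint is an occurrence in subjects and SAP 9.2 promises categories, but no qualifying change is defined and no listed table counts subjects. Table 12.8 can reveal a large rise at a scheduled visit. It cannot give n/N or show whether the subject began normal or already raised, and it has no assigned place for unscheduled values.

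The construction in step 3 shows the size: the same table is compatible with 2% and with 20% of 50 subjects affected. It assumes rises of equal size and no other change, and it illustrates the ambiguity rather than predicting a result.

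The HCV point is secondary. Eligibility of HCV-positive subjects is clear, but their share is not given, and the documents do not show that pooling matters for creatinine or BUN. The main conclusion does not depend on it.

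**What to change.** In SAP 9.2 and 9.3.2, and in the table list in 11.1:

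1. For each renal and hepatic parameter, add a shift table of baseline against worst post-baseline value, in categories relative to the laboratory's upper limit of normal. Take the worst value over all scheduled and unscheduled visits. Protocol 13.3 already requires laboratory ranges from the sites.
2. Report the number and percentage of subjects with at least one qualifying elevation that is new or increased relative to baseline, with an exact 95% interval. State whether the interval is one- or two-sided. Use as denominator the Safety Population subjects with a baseline and at least one later value, and show how many lack them.
3. Have the sponsor fix the qualifying multiples before database lock, as reporting flags only. The documents supply none, so they are a judgement to record.
4. Keep table 12.8 as supportive.
5. As a minor addition, show the hepatic rows by baseline HCV antibody status, give the number in each group, and amend SAP 6.3 to match.

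The cost is one or two extra tables, some SAP text and agreement on the multiples. No new data are needed.

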9.3.3 Vital Signs

Vital signs will be summarized by nominal study visit and change from baseline.

10. INTERIM AND END-OF-STUDY ANALYSES

CONFIDENTIAL

10.1 Interim Analysis

No interim efficacy analysis is planned for this study.

10.2 End-of-Study Analysis

A final analysis is planned after the last patient completes or discontinues the study and the resulting clinical database has been cleaned, quality checked, and locked.

